2. ABBREVIATIONS

Abbreviations pertain to the Statistical Analysis Plan (SAP) only (not the tables, figures and listings [TFLs]).

| | |
|---------------------------|---|
| AE | Adverse event |
| AUC | Area under the concentration versus time curve |
| AUC(0-t _{last}) | Area under the concentration versus time curve from time zero to time t, where t is the last time point with a measurable concentration |
| BID | Twice daily |
| BQL | Below the quantifiable lower limit of the assay |
| C _{max} | Maximum observed drug concentration |
| CI | Confidence interval |
| CL/F | Apparent total body clearance of drug calculated after extra-vascular administration |
| CRF | Case Report Form |
| CSR | Clinical Study Report |
| CSII | Continuous subcutaneous insulin infusion |
| CRU | Clinical Research Unit |
| CV | Coefficient of variation |
| Early tR _{max50} | Time of 50% of maximum GIR before R _{max} |
| ECB | Early clinical biometrics |
| ECG | Electrocardiogram |
| e.g. | For example (Latin: exempli gratia) |
| GIR | Glucose infusion rate |
| ICH | International Conference on Harmonisation |
| Late tR _{max50} | Time of 50% of maximum GIR after R _{max} |
| LLOQ | Lower limit of quantitation |
| LS | Least square |
| MDI | Multiple daily injections |
| MedDRA | Medical Dictionary for Regulatory Activities |
| NA | Not applicable |
| PD | Pharmacodynamic |

| | |
|-------------|--|
| PK | Pharmacokinetic |
| QTcB | QT interval corrected using Bazett's formula |
| QTcF | QT interval corrected using Fridericia's formula |
| R_{\max} | Maximum glucose infusion rate |
| SAP | Statistical Analysis Plan |
| SC | Subcutaneous |
| SD | Standard deviation |
| SMPG | Self-monitored plasma glucose |
| TDD | Total daily dose |
| T2DM | Type 2 diabetes mellitus |
| TID | Thrice daily |
| TFLs | Tables, Figures, and Listings |
| $t_{1/2}$ | Half-life associated with the terminal rate constant (λ_z) in non-compartmental analysis |
| t_{\max} | Time of maximum observed drug concentration |
| tR_{\max} | Time of maximum glucose infusion rate |
| V_z/F | Apparent volume of distribution during the terminal phase after extra-vascular administration |
| WHO | World Health Organization |

3. INTRODUCTION

This SAP has been developed after review of the Clinical Study Protocol (final version dated 29 April 2015 and amendment (a) dated 24 August 2015).

This SAP describes the planned analysis of the safety, tolerability and pharmacokinetic (PK) and pharmacodynamic (PD) data from this study. A detailed description of the planned TFLs to be presented in the clinical study report (CSR) is provided in the accompanying TFL shell document.

The intent of this document is to provide guidance for the statistical and PK analyses of data. In general, the analyses are based on information from the protocol, unless they have been modified by agreement between Eli Lilly and Company and Covance Early Clinical Biometrics (ECB). A limited amount of information concerning this study (e.g., objectives, study design) is given to help the reader's interpretation. This SAP must be signed off prior to first subject administration for this study. When the SAP and TFL shells are agreed upon and finalized, they will serve as the template for this study's CSR.

This SAP supersedes the statistical considerations identified in the protocol; where considerations are substantially different, they will be so identified. If additional analyses are required to supplement the planned analyses described in this SAP, they may be performed and will be identified in the CSR. Any substantial deviations from this SAP will be agreed upon between Eli Lilly and Company and Covance ECB and identified in the CSR. Any minor deviations from the TFLs may not be documented in the CSR.

This SAP is written with consideration of the recommendations outlined in the International Conference on Harmonisation (ICH) E9 Guideline entitled Guidance for Industry: Statistical Principles for Clinical Trials¹ and the ICH E3 Guideline entitled Guidance for Industry: Structure and Content of Clinical Study Reports².

4. STUDY OBJECTIVES

Primary Objectives

Part A: to compare the t_{max} of a 100-U bolus of U-500R (500 U/mL) administered via single subcutaneous (SC) injection versus a 100-U bolus of U-500R administered via continuous subcutaneous insulin infusion (CSII) in high-dose insulin-treated, obese subjects with type 2 diabetes mellitus (T2DM).

Part B: to evaluate the area under the concentration versus time curve (AUC) from time zero to 24 hours postdose (AUC[0-24]), maximum drug concentration (C_{max}), and maximum glucose infusion rate (R_{max}) of U-500R at steady state following thrice daily (TID) or twice daily (BID) SC dosing in the study population.

Secondary Objectives

Part A: to compare the time of maximum glucose infusion rate (GIR) ($t_{R_{max}}$) and exposure (AUC from time zero to time t , where t is the last time point with a measurable concentration [$AUC(0-t_{last})$]) of a 100-U bolus of U-500R administered via single SC injection versus CSII in the study population.

Part B: to evaluate the time of C_{max} (t_{max}), total amount of glucose infused (G_{tot}) and $t_{R_{max}}$ of U-500R at steady state following TID or BID SC dosing in the study population.

Exploratory Objectives

Other PK and PD parameters may be evaluated including but not limited to:

Part A: half-life associated with the terminal rate constant in no ncompartmental analysis ($t_{1/2}$), apparent total body clearance of drug calculated after extra -vascular administration (CL/F), and apparent volume of distribution during the terminal phase after extra -vascular administration (V_z/F), time of last GIR measurement ($t_{R_{last}}$), the time of first change of GIR postdose ($t_{R_{onset}}$), the time of 50% of maximum GIR before R_{max} (early $t_{R_{max50}}$), and the time of 50% of maximum GIR after R_{max} (late $t_{R_{max50}}$) in the study population.

Part B: AUC of U-500R over each dosing interval and over each meal at steady state following TID or BID SC dosing in the study population.

5. STUDY DESIGN

This is a 2-part, Phase 1 (postmarketing), single-center, 3-period, 4-sequence, randomized, open-label, crossover euglycemic clamp study in high-dose insulin-treated, obese subjects with T2DM. Part A (Periods 1 and 2) will compare the PK and PD of a 100-U bolus of U-500R administered via single SC injection versus a 100-U bolus of U-500R administered via CSII. Subjects completing Part A will transition to Part B (Period 3), which will evaluate the PK and PD characteristics of U-500R administered by TID and BID multiple daily injections (MDIs) under steady-state conditions.

Up to 32 subjects may be enrolled to achieve a target of approximately 24 completing all 3 periods of the study.

Subjects will be randomly assigned to 1 of 4 dosing sequences (Table 1.). Each subject will be administered 100 U of U-500R by single SC injection, and 100 U of U-500R by CSII in Part A and either TID U-500R or BID U-500R in Part B.

Table 1. Dosing Schedule

| Sequence | Part A | | Part B |
|----------|----------|----------|----------|
| | Period 1 | Period 2 | Period 3 |
| 1 | SC | CSII | TID |
| 2 | CSII | SC | BID |
| 3 | SC | CSII | BID |
| 4 | CSII | SC | TID |

Abbreviations: BID=twice-daily administration of U-500R; CSII=100 U U-500R administered via continuous subcutaneous insulin infusion; SC=100 U U-500R administered via single subcutaneous injection; TID=thrice-daily administration of U-500R

[figure not shown]

Figure 1. Study Design

6. TREATMENTS

The following is a list of the study treatment abbreviations that will be used in the TFLs.

| Study Treatment Name | Treatment order in TFL |
|---------------------------|------------------------|
| 100-U bolus U-500R (SC) | 1 |
| 100-U bolus U-500R (CSII) | 2 |
| U-500R (BID) | 3 |
| U-500R (TID) | 4 |

7. SAMPLE SIZE JUSTIFICATION

The primary objective of Part A of the study is to compare the t_{max} of U-500R administered by single SC injection or CSII. Up to 32 subjects may be enrolled to ensure that approximately 24 subjects complete the study.

The sample size is based on a calculation of precision of the t_{max} . Intra-subject variability for t_{max} has not been assessed previously. Based on an assumption of an intra-subject variability estimate of 20% for t_{max} , a sample size of 24 completed subjects in Part A will provide approximately 90% coverage probability that the half-width of the 90% confidence interval (CI) for the ratio of

geometric means for t_{max} will be within 0.116 in the log scale, which corresponds to approximately 12% of the geometric mean ratio estimate in the natural scale.

If any subjects discontinue the study prior to completion of the 3 periods, the replacement subjects who are enrolled will assume the discontinued subjects' randomization schedule and will complete all 3 periods.

8. DEFINITION OF ANALYSIS POPULATIONS

The "Safety" population will consist of all subjects who received at least one dose of study drug, and have at least one postdose safety assessment.

The "Pharmacokinetic" population will consist of all subjects who received at least one dose of study drug and have evaluable PK data.

The "Pharmacodynamic" population will consist of all subjects who received at least one dose of study drug and have evaluable PD data.

All protocol deviations that occur during the study will be considered for their severity/impact and will be taken into consideration when subjects are assigned to analysis populations.

9. STATISTICAL METHODOLOGY

9.1 General

Data listings will be provided for all data that is databased. Summary statistics and statistical analysis will only be presented for data where detailed in this SAP. For continuous data, summary statistics will include the arithmetic mean, arithmetic standard deviation (SD), median, min, max and N; for log-normal data (e.g. the PK parameters: AUCs and C_{max}) the geometric mean and geometric coefficient of variation (CV%) will also be presented. For categorical data, frequency count and percentages will be presented. Data listings will be provided for all subjects up to the point of withdrawal, with any subjects excluded from the relevant population highlighted. Summary statistics and statistical analyses will generally only be performed for subjects included in the relevant analysis population.

Mean change from baseline is the mean of all individual subjects' change from baseline values. Each individual change from baseline will be calculated by subtracting the individual subject's baseline value from the value at the timepoint. The individual subject's change from baseline values will be used to calculate the mean change from baseline using a SAS procedure such as Proc Univariate.

The TFLs will be programmed using SAS® Version 9.3 or greater.

9.2 Demographics and Subject Disposition

Subject disposition will be listed. The demographic variables age, sex, race, ethnicity, country of enrollment, site ID, body weight, height and body mass index will be summarized and listed.

Screening HbA1c, HbA1c $>8.0\%$, HbA1c $\leq 8.0\%$, fasting blood glucose, duration of T2DM and prestudy insulin treatment will be summarized and listed.

9.3 Pharmacokinetic Assessment

9.3.1 Pharmacokinetic Analysis

For the primary analysis, serum immunoreactive concentrations of insulin will be corrected using C-peptide data. Specifically, drug insulin concentrations will be calculated as the difference between total insulin and endogenous insulin, which in turn will be estimated with the C-peptide concentration data using Owens method (Owens 1986) with the following equation:

$$\text{Drug insulin} = \text{Total insulin} - F * \text{C-peptide}$$

where F is the average of the ratios of insulin to C-peptide at baselines (-0.5, and 0 hour) and will be calculated for the subject per the following rule:

1. If there is BQL values for insulin or C-peptide, set them to $\frac{1}{2}$ LLOQ.
2. Take the mean of the ratios of insulin to C-peptide at the two pre-dose time points (-0.5h, and 0h) during the single SC injection period as the F for the subject.

Pharmacokinetic parameter estimates will be calculated using non-compartmental methods of analysis in validated software (Phoenix WinNonlin Version 6.3, Pharsight Corporation, USA or later). The analyses will be performed according to the Lilly Global Pharmacokinetics, Pharmacodynamics, and Pharmacometrics Divisional Standard Operating Procedures. The actual validated software version used when actual analyses are conducted will be specified in the clinical study report. C-peptide may be used to correct serum immunoreactive insulin concentrations for endogenous insulin.

The primary parameter for analysis in Part A will be t_{\max} . Other noncompartmental parameters such as C_{\max} , AUC from time zero to infinity ($AUC[0-\infty]$), $AUC(0-t_{\text{last}})$, half-life associated with the terminal rate constant in noncompartmental analysis ($t_{1/2}$), the last time point with a measurable concentration (t_{last}), apparent total body clearance of drug calculated after extra-vascular administration (CL/F), and apparent volume of distribution during the terminal phase after extra-vascular administration (V_z/F) may be reported, as appropriate.

In the treatment of CSII, the PK profile of insulin via SC injection can be corrected by subtracting baseline concentration, given steady-state of infused basal insulin via CSII will be reached after 12hrs.

The primary PK parameters for Part B will be $AUC(0-24)$ and C_{\max} ; other PK parameters such as t_{\max} and AUC of U-500R over each dosing interval and over each assumed meal time period at steady state may also be reported, as appropriate.

Parameters will be individually calculated by Eli Lilly and Company and sent to Covance for statistical analysis.

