In healthy obese subjects with mean body mass index (BMI) $34.4 \pm 2.6 \text{ kg/m}^2$ (Study B5K-EW-IBHA; de la Peña et al. 2011), U-500R administered by single SC injection as

50- or 100-U doses (0.4 to 0.6 and 0.8 to 1.3 U/kg, respectively) resulted in similar overall exposure (area under the concentration versus time curve [AUC] from time zero to return to baseline) to that observed after administration of equal doses of U-100R, although maximum observed drug concentrations (C_{max}) were lower. Findings in the pharmacodynamic (PD) parameters generally reflected the pharmacokinetic (PK) findings, with similar overall effect (total amount of glucose infused [G_{tot}]) and lower maximum effect (maximum glucose infusion rate [R_{max}]). Time of maximum drug concentration (t_{max}) and the time of maximum effect (time of maximum glucose infusion rate [tR_{max}]) were significantly longer for U-500R compared to U-100R at only the 100-U dose. Duration of action (time of last glucose infusion rate measurement [tR_{last}]) and effect after the peak (time of 50% of maximum glucose infusion rate after R_{max} [late tR_{max50}]) were significantly prolonged for U-500R versus U-100R at both doses.

The only published PK study of U-500R in obese patients with type 2 diabetes mellitus (T2DM) with severe insulin resistance was a small non-clamp study conducted by Davidson et al. (2010). Nine severely insulin-resistant obese patients with T2DM and poor glycemic control were given SC boluses of 100 U of U-500R. Onset of action took place in 30 minutes or less with peak insulin levels at 5 hours and persistent elevation of insulin concentration was observed 7 hours postdose. The minimum time to reach a target plasma glucose (PG) level of less than 100 mg/dL (5.6 mmol/L) ranged from 3 to more than 7 hours (Davidson et al. 2010).

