Recently, in order to predict steady-state PK/PD of high-dose U-500R, de la Peña et al. (2014) conducted a modeling and simulation study. The model was built from 3 single-dose, crossover, euglycemic clamp PK/PD studies with human regular insulin. Healthy obese (de la Peña et al. 2011) and healthy normal-weight subjects, and patients of normal weight with type 1 diabetes mellitus (T1DM) participated in the studies. A 1-compartment, first-order absorption and elimination PK model was used and provided independent absorption rate constants for both U-500R and U-100R. An effect compartment model was used to describe the PD parameters (maximum pharmacologic effect [E_{max}] and concentration to achieve 50% E_{max}). Human regular U-500 insulin PK/PD simulation profiles were performed for once-daily, twice-daily (BID), and thrice-daily (TID) dosing regimens (de la Peña et al. 2014).

All 3 dosing regimens were predicted to achieve steady state PK by 24 hours after the initial insulin dose. At steady state, the greatest fluctuations in PK/PD parameters were observed with once-daily dosing. Conversely, BID dosing resulted in an increase in insulin concentration and effect with each dose and a stable basal effect while TID dosing resulted in sustained effects between doses. Similar to the findings of de la Peña et al. (2011), the U-500R PK/PD simulation modeling study indicated the steady state basal PD effect from both BID and TID dosing appears to support use of U-500R as insulin monotherapy, without the need for concomitant U-100 basal insulin (de la Peña et al. 2014).

Information on serious adverse events (SAEs) expected in the study population independent of drug exposure and that will be assessed by the sponsor in aggregate, periodically during the course of the study, may be found in the USPI.

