7.1.2. Part A (Study Periods 1 and 2)

Subjects will be admitted to the clinical research unit (CRU) on Day -1 of each period and be fasted from 12 hours prior to clamp initiation until completion of the clamp procedure.

All subjects will stop their prestudy U-100, U-200, and/or U-300 insulin dosing at least 15 hours prior to U-500R bolus dosing. Subjects randomized to receive U-500R by SC injection will receive a 100-U U-500R bolus administration by SC injection prior to initiation of the clamp. Subjects randomized to receive U-500R by CSII will have a U-500 OmniPod Insulin Management System (U-500 OmniPod) fitted by a qualified member of CRU staff, which will administer a 12-hour infusion of 4.25 U/h of U-500R, prior to bolus administration of 100 U of U-500R (via the same pump) and initiation of the clamp. The 4.25-U/h U-500R infusion will continue throughout the duration of the clamp following bolus administration by the U-500 OmniPod.

Overnight, between Day -1 and Day 1, all subjects will have their PG stabilized, using an insulin lispro and/or glucose drip, to a target fasting PG concentration of 120 mg/dL (6.7 mmol/L) (with an acceptable range of 100 to 130 mg/dL [5.6 to 7.2 mmol/L]).

Following bolus dose administration (or initiation of bolus dose administration for CSII), subjects will undergo a euglycemic clamp with a maximum duration of 24 hours. Following completion of the clamp procedures, subjects will be provided a meal and will be medically assessed and discharged from the CRU, unless the investigator has any safety concerns. If glucose is still being infused at the time of clamp discontinuation, the subject will be monitored for safety and will remain in the CRU until stable according to investigator judgment (see Section 10.4.1).

Blood samples will be collected prior to and during the clamp procedure (see [Attachment 1](#)) to determine serum immunoreactive insulin (IRI) and C-peptide concentrations for PK and PD analysis.

Following termination of the clamp procedure in Period 1, subjects will resume their prestudy treatment regimen (which may include basal; premixed; and/or basal/bolus U-100, U-200, and/or U-300 insulin regimens with or without antihyperglycemic agents [AHAs] as listed in Inclusion Criterion [5], Section 8.1.1) until their admission to the CRU on Day -1 of Period 2. There will be a washout period of 7 to 21 days between U-500R bolus doses in Periods 1 and 2.

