9.1. Treatment Materials and Supplies

This study involves a comparison of a 100-U bolus of U-500R administered by single SC injection versus administration via CSII and evaluation of U-500R administered SC TID and BID. [Table IBHG.9.1](#) shows the treatment regimens.

Table IBHG.9.1. Investigational Product Regimens

Regimen	Dose	Administration route	Time of administration
Part A	U-500R SC bolus	100-U	Single SC injection Prior to initiation of euglycemic clamp
	U-500R basal infusion plus U-500R CSII bolus	4.25 U/h basal and 100-U bolus	CSII 12 hour infusion of 4.25 U/h U-500R prior to 100-U bolus dose and initiation of euglycemic clamp (with continued 4.25-U/h U-500R infusion)
	U-500R TID	Per titration algorithm (TID, injectable solution)	Multiple daily SC injection Recommended 07:00, 12:00, and 18:00 hours, approximately 30 minutes prior to morning meal, midday meal, and evening meal, respectively ^a
Part B	U-500R BID	Per titration algorithm (BID, injectable solution)	Multiple daily SC injection Recommended 07:00 and 18:00 hours, approximately 30 minutes prior to morning meal and evening meal, respectively ^a

Abbreviations: BID = twice daily; CSII = continuous subcutaneous insulin infusion; SC = subcutaneous;

TID = thrice daily; U-500R = human regular U-500 insulin.

^a If a meal is skipped, insulin dose should be reduced by 50%.

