11.1. Determination of Sample Size

The primary objective of Part A of the study is to compare the t_{max} of U-500R administered by single SC injection or CSII. Up to 32 subjects may be enrolled to ensure that approximately 24 subjects complete the study.

The sample size is based on a calculation of precision of the t_{max} . Intra-subject variability for t_{max} has not been assessed previously. Based on an assumption of an intra-subject variability estimate of 20% for t_{max} , a sample size of 24 completed subjects in Part A will provide approximately 90% coverage probability that the half-width of the 90% confidence interval (CI) for the ratio of geometric means for t_{max} will be within 0.116 in the log scale, which corresponds to approximately 12% of the geometric mean ratio estimate in the natural scale.

If any subjects discontinue the study prior to completion of the 3 periods, the replacement subjects who are enrolled will assume the discontinued subjects' randomization schedule and will complete all 3 periods.

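### Part A: only the CSII period carries a U-500R basal, the planned PK correction for it is optional and loosely defined, and the Gtot and Rmax ratios have no visible correction

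*SAP*

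**What the plan says.** Protocol 7.1.2 gives the SC period a single 100-U injection and no U-500R basal. The CSII period has 12 h of U-500R at 4.25 U/h and then the 100-U bolus; after that, "The 4.25-U/h U-500R infusion will continue throughout the duration of the clamp following bolus administration by the U-500 OmniPod". Table IBHG.9.1 describes this regimen as "U-500R basal infusion plus U-500R CSII bolus". In both periods glucose is stabilised overnight "using an insulin lispro and/or glucose drip".

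The objectives (Protocol 6.1 and 6.2, SAP 4) name only the two 100-U boluses. For Part A, tmax is primary; tRmax and AUC(0-tlast) are secondary.

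The basal appears once in the analysis text, in SAP 9.3.1: "In the treatment of CSII, the PK profile of insulin via SC injection can be corrected by subtracting baseline concentration", with the reason "given steady-state of infused basal insulin via CSII will be reached after 12hrs". The analysis sections of the protocol (11.2.4 and 11.2.5) do not mention it. SAP 9.3.2 then fits log-scale models to tmax, AUC(0-tlast), AUC(0-∞) and Cmax without saying whether the CSII values are corrected. SAP 9.4.1 takes Gtot, Rmax and tRmax from the LOESS-fitted glucose infusion rate, with Gtot covering the whole clamp. SAP 9.4.2 presents the Gtot and Rmax ratios as a comparison of administration methods.

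**The concern.** Without a defined correction, the SC/CSII ratios mix two things: how the bolus was delivered, and whether a basal was running. Four features of the plan leave this open.

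- The correction is permitted, not required. The sentence speaks of a profile from SC injection within the CSII treatment, and it does not say which parameters use the corrected profile.
- The -0.5 and 0 h baselines are defined only for the C-peptide factor F. F comes from the SC period and is not designed to remove infused insulin.
- The 12-h steady state is asserted. Pre-bolus samples are scheduled, but no check is planned with them.
- The PD ratios have no visible basal handling. Protocol 5.2 raises the possibility of greater prandial effect by CSII; added basal raises the glucose requirement in that period and could mimic part of it.

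At stake are AUC(0-tlast), which serves a named secondary objective, and the additional planned ratios for Cmax, AUC(0-∞), Gtot and Rmax. The infusion runs until the last sample, so the CSII terminal phase used for AUC(0-∞), t½, CL/F and Vz/F is not that of the bolus alone.

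**Working it through.** **The plan's own figure.** Protocol 11.1 says the 90% CI half-width for the tmax ratio "will be within 0.116 in the log scale", with 24 completers, 20% intra-subject variability and about 90% probability. With σ = √ln(1 + 0.20²) = 0.198, half-width = t(0.95, 22) × σ × √(2/24) = 1.717 × 0.198 × 0.2887 = 0.0982. Multiplying by √(χ²(0.90, 22)/22) = √(30.81/22) = 1.183 gives 0.116. It reproduces, and it is the yardstick for any shift in tmax.

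**Basal load.** Before the bolus: 4.25 × 12 = 51 U. During a 24-h clamp: 4.25 × 24 = 102 U. If exposure is proportional to dose, the uncorrected SC/CSII ratio for identical boluses is 100/(100 + 102) = 0.495. Over 12 h it is 100/151 = 0.66, and over 16 h 100/168 = 0.60.

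**What subtraction leaves.** Assumptions, none taken from trial data: linear PK, one compartment with first-order absorption and elimination, equal bioavailability and clearance, identical boluses (true ratio 1.00), and basal absorbed like the bolus. The peak is set at 2 h or 5 h, and the elimination/absorption rate ratio r at 1 to 5. The 5-h value is from Protocol 5.1, which reports "peak insulin levels at 5 hours and persistent elevation of insulin concentration was observed 7 hours postdose" in nine patients given 100 U; the 2-h value is an assumed fast case.

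Let g(t) be the unit-dose curve and G(t) its integral. The bolus is 100·g(t) and the basal is 4.25·G(t + 12). For r = 1, G(12) = 1 − e^(−12k)(1 + 12k) with k = 1/peak time. At 5 h this is 1 − e^(−2.4) × 3.4 = 0.692; at 2 h it is 1 − e^(−6) × 7 = 0.983.

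One case in full (5-h peak, r = 1): over 0-24 h the bolus area is 95.23, the basal area 93.66, and the predose level times 24 is 70.54.
- Uncorrected: 95.23/(95.23 + 93.66) = 0.504.
- Subtracted: 95.23/(95.23 + 93.66 − 70.54) = 0.805.

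| Quantity (r = 1 to r = 5) | 2-h peak | 5-h peak |
|---|---|---|
| Basal at 0 h, share of plateau | 98% to 89% | 69% to 53% |
| AUC(0-24) ratio, uncorrected | 0.50 | 0.50 |
| AUC(0-24) ratio, subtracted | 0.98 to 0.92 | 0.81 to 0.75 |
| Delay in CSII tmax | about 0.02 h or less | 0.33 to 0.70 h |

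Subtracting a constant cannot move tmax, so the delay is the same with or without it. At a 5-h peak the delay is 0.065 to 0.130 in logs, against 0.116. On the scheduled sampling times the observed peak stays at 5 h for r = 1 and 2 and moves to 6 h for r = 3 and 5.

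At a 5-h peak the offset left at 24 h after subtraction is 1.2 to 1.6 times the bolus concentration, so a terminal slope fitted there would be unreliable.

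**Support for 12 h.** The only other steady-state time in the documents is in Protocol 5.1: "All 3 dosing regimens were predicted to achieve steady state PK by 24 hours after the initial insulin dose". It comes from modelling of injection regimens. It neither contradicts nor supports 12 h for an infusion.

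**PD.** The documents give no relation between insulin level and glucose infusion rate from which a bias in Gtot, Rmax or tRmax could be computed.

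**The case against.** The strongest reply is that the slow case is extrapolated. A 5-h peak after 100 U in nine patients need not describe a slow infusion, and Protocol 5.1 reports that U-500R peaked later than U-100R only at the 100-U dose. If the bolus peaks at 5 h but the basal is absorbed as with a 2-h peak, the same model gives a subtracted AUC(0-24) ratio of 0.98-0.90 and a tmax delay of 0.01-0.20 h. This stands: how much bias survives subtraction is unknown and may be small.

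A reader might infer that the subtraction always under-corrects. The documents do not support that. Overnight lispro, or prestudy insulin stopped as little as 15 h earlier, may still be declining at 0 h, and Protocol 7.2 says the assay is not specific to U-500R. A declining component makes constant subtraction over-correct. F may absorb an unknown part of this, so the net sign cannot be determined.

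A reader might also want a mandatory analysis that models a rising basal from each subject's own SC curve. That assumes CSII absorption equals SC absorption, which is close to what the study tests. With an SC peak of 5 h and a CSII peak of 2 h (r = 1 to 5), the true AUC(0-24) ratio is 0.95-0.83. The SAP's subtraction gives 0.94-0.76, and the rising-basal method 0.88-0.69, which is further off.

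It is also fair that the run-in itself limits the problem, that baseline reads naturally as the -0.5 and 0 h samples, that listings would show drift, and that the regimen is openly described. Sponsor SOPs and the TFL shells, which the SAP cites, were not available and may say more. None of this makes the correction mandatory or states its scope, and the visible SAP text still attributes the PD ratios to administration method.

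**Conclusion.** The point holds for AUC, Cmax and the PD ratios, as a matter between minor and should-fix. As written, the plan allows an AUC(0-24) ratio of about 0.50 or one near 1 from the same identical boluses, depending on a choice left to the analyst. After subtraction the illustrative range is 0.98-0.92 (2-h peak) to 0.81-0.75 (5-h peak), under linear kinetics with basal absorbed like the bolus; other insulin at 0 h could move it either way.

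Two stronger readings should be resisted. The primary tmax comparison is not shown to be compromised: the delay approaches or exceeds the planned half-width only if basal absorption is slow. And the 12-h steady state is not shown to be false; it is unsupported and unchecked. For Gtot and Rmax, the conclusion is that their ratios compare bolus plus basal with bolus alone. The size of that effect is unknown, and neither is a named Part A objective. tRmax is one, and it comes from the same clamps.

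**What to change.** In SAP 9.3.1:
- Change the permissive wording to *will be* and name the CSII-period profile.
- State that CSII AUC(0-tlast) and Cmax use the profile after subtracting the mean of the C-peptide-corrected -0.5 and 0 h values, with uncorrected values shown as supportive.
- Do not derive AUC(0-∞), t½, CL/F or Vz/F from the uncorrected CSII profile. Flag the subtracted versions as unreliable if the basal is not at plateau.
- Tabulate the scheduled CSII samples at -8, -4, -0.5 and 0 h as a plateau check. It is indicative only, given lispro and the non-specific assay. If levels are still drifting, qualify the AUC, Cmax and tmax comparisons.

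In SAP 9.4.2 and the output titles or footnotes:
- Label the Gtot and Rmax ratios (and tRlast and late tRmax50 if reported) as 100-U bolus plus 4.25 U/h basal versus 100-U bolus alone.
- Do not interpret them as an effect of administration method alone, and put the same caveat on tRmax.

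A model-based rising-basal analysis may be added as exploratory only.

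The cost is SAP wording, one table and some labels, with no new samples or subjects. The downside is a narrower PD claim.
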